#### **8.2. Off study criteria**

- 1) Death
- 2) Lost to follow up
- 3) Participation in other trials of investigational therapies

## 9. STATISTICAL CONSIDERATIONS

### 9.1 Sample Size and Power

Review of 40 patients with TTP at BJH who would have met the inclusion criteria indicates that the composite primary endpoint rate was 55% in this historical group. Assuming a 10 percent of composite primary endpoint rate in the treated group and 40 historical controls, 14 treated patients are needed to have a 90% power to detect a 45 % difference in the incidence of exacerbation at the 5% significance level. We will enroll 20 patients total and expect to enroll 12 patients per year. Therefore, recruitment may be complete within less than 2 years. The time would be reduced by participation of other regional hospitals.

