## ABSTRACT

The ART study (Adjuvant Rituximab in TTP) is a pilot safety/efficacy study of adjuvant low dose rituximab (100 mg/week x 4 doses) plus standard plasma exchange and corticosteroids for the treatment of thrombotic thrombocytopenic purpura (TTP) with severe ADAMTS13 deficiency. Results for study subjects will be compared to historical controls treated initially with plasma exchange and corticosteroids. This study proposes to test the hypothesis that adjuvant low dose rituximab may decrease the incidence of composite primary endpoint (exacerbations or refractory disease) in acquired TTP with severe ADAMTS13 deficiency. A novel ADAMTS13 assay will be used to identify patients with TTP and severe ADAMTS13 deficiency for enrollment, and to assess the utility of ADAMTS13 as a biomarker for response to therapy and prognosis.

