## **3. STUDY POPULATION**

### **3.1 Inclusion criteria**

- 1) Age  $\geq$ 18 years
- 2) Diagnosis of suspected TTP
  - a. Platelet count of  $<80,000/\mu\text{L}$  for newly diagnosed patients and  $<120,000/\mu\text{L}$  for relapsed patients
  - b. Microangiopathic hemolytic anemia (MHA) with RBC fragmentation
  - c. LDH  $>1 \times \text{ULN}$
- 3) Subjects who will receive treatment for TTP with plasma exchange
- 4) Subjects who have not started the 5TH plasma exchange.
- 5) Plasma ADAMTS13 activity  $<10\%$

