### **3.2 Exclusion criteria**

- 1) Treatment for TTP within the past 2 months
- 2) Severe active infection indicated by sepsis (requirement for pressors with or without positive blood cultures) or clinical evidence of enteric infection with *E. coli* O157:H7 or related organism.
- 3) Currently under treatment for cancer or with a current diagnosis of cancer (subjects with localized skin carcinoma will be accepted)
- 4) Microangiopathic hemolytic anemia due to a mechanical heart valve
- 5) Severe hypertension, as defined by systolic BP  $>180$  AND diastolic BP  $>120$ , or papilledema
- 6) Organ or stem cell transplant

- 7) Use of calcineurin inhibitors (e. g., sirolimus, tacrolimus, cyclosporin A) within 6 months prior to diagnosis
- 8) Disseminated intravascular coagulation, as defined by:
  - a. INR >2.0 (unrelated to anticoagulation, unresponsive to vitamin K) **or**
  - b. Fibrinogen <100 mg/dL
- 9) Pregnancy
- 10) Known congenital TTP.
- 11) Rituximab within the previous year.
- 12) HIV history or positive serology
- 13) History of hepatitis B or positive serology for HBsAg or Anti-HBc
- 14) Persistent or unexplained platelet count below 150,000/ $\mu$ L within 3 months of current TTP presentation
- 15) Hypersensitivities or allergies to murine and/or humanized antibodies
- 16) Current participation in trials of investigational therapies or devices, except that investigational central catheters are not exclusions

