#### **4. STUDY ENROLLMENT**

##### **4.1 Recruitment and screening**

Subjects will be recruited through the Transfusion Medicine or Hematology Consult services at Washington University and up to 5 additional sites. A potentially eligible subject will be identified by his or her physician. Once a potentially eligible subject is identified, and after the treating staff has obtained permission from the subject to be contacted, a member of the study staff will contact the subject, describe the study, and obtain consent.

After signing the consent form the subject will be assigned a study ID number and study staff will determine if the subject is eligible based on his or her medical history and laboratory results. A subject is considered enrolled in the study after the informed consent document is signed by the subject and the subject meets all eligibility criteria. Within one day (Monday-Friday) after enrollment, the site should submit a copy of the Inclusion/Exclusion Criteria Checklist that has been signed by a site investigator to the Washington University Clinical Coordinating Center.

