### 9.2 Data analysis

Fisher Exact tests will be used to compare the incidence of the composite primary endpoint, Durable Treatment Response, Relapse, treatment-related adverse events and 4-week, 1-year and 2-year incidence of death between the treated group and historical controls. We will consider Chi-Square test to examine differences in the type and severity of adverse events between the treated group and historical controls.

The time to Durable Treatment Response and Relapse will be described by Kaplan-Meier estimators and log rank tests. The effects of patient characteristics will be evaluated with Cox proportional hazards models. Numbers of plasma exchanges to Durable Treatment Response will be compared with non-parametric tests (e.g. Kruskal-Wallis analysis of variance).

The value of ADAMTS13 biomarker data for predicting Exacerbation, Durable Treatment Response or Relapse will be analyzed by logistic regression. The relationship between ADAMTS13 biomarker parameters and platelet count, LDH or B cell levels will be investigated with linear regression models.

Rituximab levels and the extent of B cell depletion will be analyzed as stratified categorical data with Cochran-Mantel-Haenszel statistics.

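### The 40 historical controls are not said to have passed the exclusion criteria or the enrolment filter applied to treated patients, and no planned analysis of the composite checks comparability

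*Combined protocol and SAP*

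**What the plan says.** The Abstract compares study subjects with "historical controls treated initially with plasma exchange and corticosteroids". Section 9.1 gives the source of the control rate: "Review of 40 patients with TTP at BJH who would have met the inclusion criteria", with a composite rate of 55% (22 of 40). I found no other description of these patients.

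Treated patients pass further filters. Section 3.2 lists 16 exclusions, among them "Treatment for TTP within the past 2 months" (exclusion 1) and "Persistent or unexplained platelet count below 150,000" per µL within 3 months of presentation (exclusion 14). Inclusion criterion 4 opens "Subjects who have not started the 5" and refers to the fifth plasma exchange. Under Section 4.1 a subject is enrolled once "the informed consent document is signed by the subject and the subject meets all eligibility criteria". The Definitions set Day 1 at the first plasma exchange.

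For the analysis, Section 9.2 says "Fisher Exact tests will be used to compare the incidence of the composite primary endpoint", along with other incidences, between the treated group and the controls. Patient characteristics appear only in Cox models, introduced directly after the two time-to-event endpoints. Logistic regression is reserved for ADAMTS13 as a predictor of Exacerbation, Durable Treatment Response or Relapse.

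**The concern.** The trial is not randomised, so the primary result depends on 55% being the rate that the enrolled patients would have had without rituximab. Two gaps bear on this.

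**Exclusions.** The protocol separates inclusion (3.1) from exclusion (3.2), and Section 9.1 names only inclusion. Exclusion 14 uses 150,000/µL, the same platelet level that defines Treatment Response. Exclusion 1 removes recently treated TTP. Both plausibly relate to the composite.

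**Entry.** Day 1 is a common time origin, but the groups are conditioned differently after it. A treated patient must survive to consent and confirmed eligibility before the fifth exchange. Inclusion criterion 4 cannot impose this on a chart control: with no enrolment date, every patient satisfies it at some time. A control who died before a treated patient could have enrolled has no treated counterpart, and would count as an event if the definition of Refractory TTP is read literally. A control who responded very early may also lack a counterpart, which pushes the other way.

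If some of the 40 are patients the trial would not have enrolled, a modest difference could reflect selection, and no planned analysis of the composite would show it.

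**Working it through.** **Inputs.** From Section 9.1: 40 controls, 55% control rate (22/40), 10% assumed treated rate, 14 treated needed for 90% power at 5%, 20 to be enrolled. From Section 9.2: Fisher exact test. Sidedness is not stated; two-sided is assumed. All other true rates below are my assumptions.

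**The plan's own figure.** Pooled two-sided z-test, 14 versus 40:
- pooled rate = (14×0.10 + 40×0.55)/54 = 0.433
- null SE = √[0.433×0.567×(1/14 + 1/40)] = 0.1539
- alternative SE = √(0.09/14 + 0.2475/40) = 0.1123
- power = Φ[(0.45 − 1.96×0.1539)/0.1123] = Φ(1.32) = 90.7%

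The stated 14 reproduces. Exact two-sided Fisher power is 84.2% at 14 and 94.8% at the planned 20. The sample-size arithmetic is not the issue.

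**Chance of a significant benefit with no drug effect.** Sum Bin(a; 20, pT) × Bin(c; 40, 0.55) over all (a, c) with Fisher p ≤ 0.05 and a/20 < c/40:

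| Enrolled population's true rate | Controls' true rate | Chance |
|---|---|---|
| 55% | 55% | 1.5% |
| 50% | 55% | 3.5% |
| 45% | 55% | 7.1% |
| 40% | 55% | 13.4% |
| 60% | 55% | 0.6% |
| 65% | 55% | 0.2% |

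If both groups share 50%, 45% or 40%, the chance stays at 1.4% to 1.6%. The rise therefore comes from the gap between the groups, not from the level.

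An illustration in chart terms (assumed): if 20% of controls are ineligible and 80% of those had the event, the eligible rate is (0.55 − 0.20×0.80)/0.80 = 48.75%, and the chance is 4.2%.

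**How many charts it takes.** Two-sided Fisher p, removing ineligible controls who had the event:

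| Treated events | vs 22/40 | Significance first lost at |
|---|---|---|
| 5/20 | 0.032 | 21/39 (1 removed), p = 0.052 |
| 4/20 | 0.013 | 16/34 (6 removed), p = 0.079 |
| 3/20 | 0.005 | 13/31 (9 removed), p = 0.064 |
| 2/20 | 0.001 | 10/28 (12 removed), p = 0.051 |

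Conversely, 6/20 (p = 0.100 vs 22/40) becomes significant if four controls without the event are removed (22/36, p = 0.0496).

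**The case against.** Section 9.1 may simply mean full eligibility, and one sentence from the sponsor could settle that; how the charts were screened cannot be seen from the documents. The controls are not undefined: their hospital is named, and the inclusion criteria fix age, platelets, haemolysis, LDH and ADAMTS13 activity below 10%. Day 1 can be read from any chart, so the entry mismatch covers at most the first four exchanges. The documents do not say how many deaths or responses fall there. How death before response is scored is also unsettled: Section 1.2.1 lists death as a separate endpoint and Section 8.2 makes it an off-study criterion. All of this stands, and it limits the point.

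The rate gaps are assumed, and fragility to a single chart arises only at the significance boundary. If the true treated rate is 10%, exactly 5/20 has a 3.2% chance, while 3/20 or fewer has 86.7%. That also stands.

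A reader might infer that later rituximab in the controls would flatter the new treatment, since Section 2.4 calls salvage rituximab the current standard of care and the Abstract says only that controls were treated initially without it. The documents do not support this. Rituximab given after an exacerbation cannot undo an event already counted. Given earlier and if effective, it would tend to lower the control rate and work against a positive result.

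One could say the Cox models already address patient characteristics. They follow the time-to-event endpoints, state no adjustment of the group comparison, and do not cover the composite. Pilot status does not remove the need either: the plan states a hypothesis, a power and a significance level for this comparison.

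**Conclusion.** The point holds as a gap in how the comparator is defined and checked, and should be fixed. As written, treated patients are filtered by Section 3.2 and by reaching enrolment before the fifth exchange. The controls are not said to have been filtered by either, and no planned analysis of the composite compares the groups at baseline, adjusts, or tests sensitivity.

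A reader might go further and conclude that the 40 include ineligible patients, or that 55% is inflated. The documents show neither, and the direction of any bias cannot be determined from them.

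Under assumed gaps of 5 to 15 percentage points with the enrolled population lower, the chance of a spurious significant benefit rises from 1.5% to between 3.5% and 13.4%. With the enrolled population 5 or 10 points higher it falls to 0.6% or 0.2%. These figures assume a two-sided Fisher test, 20 versus 40, and binomial counts in both groups. The planned effect of 2/20 is robust; the exposure is to a modest result such as 5/20.

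**What to change.** In Sections 9.1 and 9.2, before outcomes are compared:

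1. **Re-screen** the 40 charts against both 3.1 and 3.2, from baseline data only, by existing study staff without the outcome data. Keep charts that lack a test and report how many. Use the eligible controls in the primary Fisher test, and restate the control rate and power.
2. **Report** the controls' admission dates, how many received rituximab before day 60, and a baseline table of both groups.
3. **Align entry** in one sensitivity analysis with the same rule in both groups: match or weight controls to the treated patients' distribution of exchanges completed at enrolment, counting a control at a given exchange number only if alive and eligible then. State how death before Treatment Response is scored in the composite, and apply it identically in both groups.
4. **Keep Fisher as primary**, and add a supporting exact analysis stratified by first versus relapsed episode.

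A subset of the more recent half of controls is optional. So is one restricted to treated patients from the control hospital, which is relevant because recruitment covers "Washington University and up to 5 additional sites".

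**Cost.** A re-check of 40 charts and SAP wording; no new patients. Some controls may be lost. At a 10% treated rate, power goes from 94.8% to, for example, 87.0% with 36 controls at 50% or 81.9% with 16/34; a heavier loss (13/31) gives 66.5%. If aligning entry leaves the equivalent of 30 or 25 controls at 55%, power is 92.5% or 89.5%. Stratifying costs nothing if the strata are balanced (95.0%), and gives 87.5% if treated patients split 5/15 and controls 30/10 (assumed).

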## DEFINITIONS

**Day 1:** The first day a subject receives plasma exchange for treatment of TTP.

**Treatment Response:** 2 consecutive days with platelet count  $\geq 150,000/\mu\text{L}$

**Durable Treatment Response:** Treatment Response that persists for  $\geq 30$  days after discontinuation of plasma exchange.

**Exacerbation:** Recurring TTP  $\leq 30$  days after a Treatment Response and discontinuation of plasma exchange.

[figure not shown]
**Refractory TTP:** Failure to achieve a Treatment Response by day 28, or failure to achieve a Durable Treatment Response by day 60.

**Composite Primary Endpoint:** Exacerbation or Refractory TTP.

**Relapse:** Recurring TTP  $> 30$  days after Treatment Response.

**Observation Period:** The interval of 2 years after a subject first achieves a Durable Treatment Response.

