### 1.2 Secondary Endpoints

#### 1.2.1 Clinical and Safety Endpoints

- Incidence of Durable Treatment Response
- Number of days to Durable Treatment Response
- Number of plasma exchanges to Durable Treatment Response
- Incidence of relapse
- Numbers of days to relapse
- 4 week, 1 year and 2 year incidence of death
- Incidence, type and severity of treatment-related adverse events

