## 2. BACKGROUND AND SIGNIFICANCE

### 2.1. Utility of ADAMTS13 data in TTP

The introduction of plasmapheresis with plasma exchange has increased survival in patients with TTP from less than 10 percent to 80 percent and is the only therapy demonstrated to be effective in a randomized clinical trial (Rock 1991). Plasma exchange rapidly restores circulating levels of the von Willebrand factor cleaving protease, ADAMTS13, and removes inhibitors to the enzyme. Although clearly beneficial, plasma exchange does not correct the primary cause of the disorder. More than 30% of patients with TTP have at least one relapse within 2 years (Kremer 2008). In addition plasma exchange may itself cause significant morbidity. One study documents a 31% risk for major complications, including a 3% fatality rate (McMinn 2003).

An autoimmune etiology of acquired TTP in adults is strongly supported by the finding of circulating ADAMTS13 inhibitors due to IgG autoantibodies. These inhibitors are found in 48 to 80% of individuals with idiopathic TTP (Moake 2002, Tsai 2003, Veyradier 2001). ADAMTS13, a von Willebrand factor-cleaving protease, regulates the size of von Willebrand factor (VWF) multimers. Deficiency of ADAMTS13 activity is associated with persistence of ultra large molecular weight VWF (ULVWF) multimers. ULVWF avidly binds to platelets, leading to

microvascular platelet deposition, the hallmark of TTP. Subsequent series identified severe ADAMTS13 activity deficiency in 30% to 80% of cases of TTP (Lammle 2005).

Although severe deficiency of ADAMTS13 activity (<5%) appears to be specific for TTP, the syndrome can also be seen in subjects with less severe deficiency and even normal levels of ADAMTS13 making diagnostic decisions difficult (George 2004). However, the risk of relapse is higher (~45%) for patients with persistent severe ADAMTS13 deficiency during remission, and essentially all of these patients have severe ADAMTS13 deficiency when they relapse (Zheng 2004). ADAMTS 13 inhibitors also correlate with relapses, delayed response to plasma exchange, refractory disease, and early death (Zheng 2004, Bohm 2005, Coppo 2006, Kremer Hovinga 2010).

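### Does the 10% treated event rate in section 9.1 ignore early deaths and so overstate the power of 20 patients?

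*Combined protocol and SAP*

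**What the plan says.** The composite primary endpoint is Exacerbation or Refractory TTP. The Definitions describe Refractory TTP as "Failure to achieve a Treatment Response by day 28, or failure to achieve a Durable Treatment Response by day 60". Death has no line of its own in the composite. It is a secondary endpoint in section 1.2.1 ("4 week, 1 year and 2 year incidence of death") and an off-study criterion in section 8.2, next to "Lost to follow up".

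Section 9.1 reports a review of 40 patients treated earlier who would have met the inclusion criteria, and "indicates that the composite primary endpoint rate was 55% in this historical group". It continues: "Assuming a 10 percent of composite primary endpoint rate in the treated group and 40 historical controls, 14 treated patients are needed". It then plans to enrol 20. Its power statement names the endpoint differently: "14 treated patients are needed to have a 90% power to detect a 45 % difference in the incidence of exacerbation". Section 9.2 states that "Fisher Exact tests will be used to compare the incidence of the composite primary endpoint" between the treated group and the historical controls. Neither section states whether the test is one- or two-sided, names an analysis set, or gives a rule for death or loss before day 60.

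Section 2.1 says that plasma exchange "has increased survival in patients with TTP from less than 10 percent to 80 percent".

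**The concern.** A patient who dies before responding has not achieved a response, so on the wording that patient is an event. The treated composite rate then cannot be lower than the rate of early death. If early mortality were anywhere near the 20% implied by section 2.1, a 10% composite rate would be unreachable and the stated power too high.

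There is also a risk of a choice made after the fact. The control result is already known (55% of 40 is 22), so an unwritten death rule could be settled once the 20 treated outcomes are in. Take 2 non-fatal events and 4 early deaths:

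- Deaths counted: 6/20 against 22/40, Fisher p = 0.100 two-sided, 0.059 one-sided.
- Deaths dropped from the treated group only: 2/16 against 22/40, p = 0.006 two-sided.
- Deaths dropped from both groups, if 4 of the 22 control events were deaths: 2/16 against 18/36, p = 0.014 two-sided.

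On that data set the rule would decide the primary comparison.

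**Working it through.** **Inputs.** Section 9.1: control rate 55% of 40, treated rate 10%, 14 needed, 20 enrolled, 5% level. Section 9.2: Fisher's exact test. Sidedness is not stated, so both are shown.

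**1. The plan's own figure.** Normal approximation with pooled variance, two-sided, 14 treated:

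- pooled rate = (22 + 1.4)/54 = 0.4333
- null SE = √[0.4333 × 0.5667 × (1/40 + 1/14)] = 0.1539
- alternative SE = √[0.55 × 0.45/40 + 0.10 × 0.90/14] = 0.1123
- power = Φ[(0.45 − 1.96 × 0.1539)/0.1123] = 90.7%

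With 13 patients the same formula gives 88.8%, so 14 is the smallest number that reaches 90%. One-sided Fisher at 14 gives 91.1%. Two-sided Fisher at 14 gives 84.2% and first reaches 90% at 16 (90.5%). The 14 is therefore reproducible, and enrolling 20 covers the choice of test.

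**2. Power of the planned 20.** Two calculations are possible. *Random controls* sums over Binomial(20, p) × Binomial(40, 0.55) and rejects when Fisher p ≤ 0.05. *Fixed controls* takes the known 22/40. With 22/40 fixed, 5/20 is significant (p = 0.032 two-sided, 0.026 one-sided) and 6/20 is not (0.100, 0.059). The cut-off is therefore 5 events for either sidedness, and power is P[Binomial(20, p) ≤ 5].

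| Treated rate | Random controls, two-sided | Random controls, one-sided | Fixed 22/40, either |
|---|---|---|---|
| 10% | 94.8% | 96.6% | 98.9% |
| 14.5% | 86.1% | 90.4% | 94.1% |
| 15% | 84.8% | 89.4% | 93.3% |
| 19% | 73.3% | 80.4% | 83.6% |
| 20% | 70.1% | 77.7% | 80.4% |
| 28% | 43.0% | 53.3% | 49.5% |

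The 14.5%, 19% and 28% rows are early mortality d of 5%, 10% and 20% plus events in 10% of survivors: d + (1 − d) × 0.10. For example, 0.05 + 0.95 × 0.10 = 0.145. With fixed controls, power stays above 90% up to a treated rate of about 16.5%.

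**3. Is 20% early mortality the plan's figure?** To make 70% or 78% an upper limit, three things must hold together: all of the 20% die before the required response and inside the day-28 or day-60 window; treated mortality equals the background figure; and the control rate stays at 55%. Section 2.1 gives no time window and describes TTP treated by plasma exchange in general. This trial excludes pressor-requiring sepsis, current cancer, transplant and disseminated intravascular coagulation (section 3.2), and a patient may enter after up to four exchanges (section 3.1). Section 2.2 cites complete remission in 95% of 73 rituximab-treated patients and complete response in 12 of 13 (92%). None of these sources measures early death in this cohort. Early mortality of 5% to 20% is an assumed range, and 20% is its pessimistic end.

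**4. What if the 55% left deaths out?** Adding 20% mortality evenly to controls gives 1 − 0.45 × 0.80 = 64%. Power with random controls is then 88.2% / 93.1% (two-sided / one-sided) at a treated rate of 20%, and 68.6% / 78.3% at 28%. The comparator moves too, so the 70% and 78% figures are not a ceiling in that case either.

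**5. The Definitions beside section 9.1.** A death before a Treatment Response fails the day-28 limb. A death after a Treatment Response but before it has lasted the required 30 days fails the day-60 limb. Section 9.1 gives the 55% as the rate of this same composite. Applied literally, the plan counts early deaths as events in both groups. Section 8.2 says when follow-up ends; it takes nobody out of the analysis.

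**The case for a change.** The strongest case for a change is that, with 20 patients and a known comparator, a classification rule should be explicit. Suppose 10% of treated survivors have an event and the 22 control events include 2, 4, 6 or 8 deaths. Counting rather than excluding deaths in both groups then changes the two-sided verdict in 4.1%, 8.7%, 18.0% and 21.5% of trials, at early mortality of 5%, 10%, 15% and 20%. Excluding deaths from the treated group only gives 3.4%, 13.2%, 27.8% and 44.1%. Even 5% mortality takes two-sided power with random controls below 90%, to 86.1%.

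The arithmetic stands, but these figures measure the effect of leaving the written definition. The plan proposes exclusion nowhere, and exclusion from one group only would contradict the Definitions. The worked example is also uncommon: 2 events with 4 deaths has probability 0.4%, 2.5% and 6.0% at early mortality of 5%, 10% and 20%.

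It is fair to say that the protocol does not confirm in words that the 40 charts were counted with deaths as events, gives no rule for loss to follow-up, and does not state sidedness. An analyst would apply one definition to both groups and could treat an undocumented response as not achieved. Sidedness does not move the cut-off at 20 against 22/40. It would move it by one event with fewer patients analysed: 5/19 gives p = 0.052 two-sided and 0.036 one-sided. The margin over 14 helps here too: at the assumed 10% rate, 16 evaluable patients still have 90.5% (two-sided) or 94.1% (one-sided).

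**Conclusion.** No change follows. No stated figure is wrong: 14 reproduces under two ordinary methods, and 20 patients exceed 90% power at the assumed 10% rate with either sidedness. That rate leaves room for 2 events of any kind in 20, so it conflicts with early mortality only above 10%, which the documents do not establish for this cohort.

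The 70.1% and 77.7% figures are correct for a 20% treated rate with controls treated as a fresh sample at 55%. They are one sensitivity point and not a limit; with the known 22/40 fixed, the figure is 80.4%. Followed as written, the plan counts a death before the required response as Refractory TTP and compares like with like. This assumes that the historical 55% was counted under the stated definition, as section 9.1 says.

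The silences on loss to follow-up, analysis set and sidedness are gaps that a competent analyst fills without altering the design of a self-described pilot. Naming exacerbation where the composite is meant is a clerical slip, since both rates behind the 45-point difference are composite rates (55% − 10%).

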### 1.1 Primary Endpoint

- Incidence of composite primary endpoint, Exacerbation or Refractory TTP

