## **2.4. Proposed Study of Low-Dose Adjuvant Rituximab for TTP**

The substitution of low dose for standard dose rituximab would reduce the drug cost 7-fold to approximately \$2,000 for a 4 week course, which approximates the cost of one plasma exchange procedure. Low dose rituximab (100 mg) may also have a decreased risk of complications. Two studies of low dose rituximab for ITP reported mainly mild infusional reactions. The rate of serious complications is probably low but not known precisely: one of 59 patients with ITP treated with low dose rituximab developed interstitial pneumonia that responded to steroids (Provan 2007, Zaja 2010).

Based on the currently available data we propose a pilot study to determine whether adjuvant low dose rituximab, in addition to standard therapy with plasma exchange and corticosteroids, can shorten the time to treatment response and reduce the risk of exacerbation for patients with TTP caused by ADAMTS 13 deficiency.

We will use a novel assay to evaluate the utility of ADAMTS 13 as a biomarker to assess the response to therapy and predict the risk of relapse. If successful this therapy would not only improve patient outcomes but also would be cost saving compared to standard dose, salvage rituximab, which is the current standard of care.

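### Does naming exacerbation, rather than the composite, in the Section 9.1 power statement leave the trial powered for the wrong outcome?

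*Combined protocol and SAP*

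**What the plan says.** Section 9.1 (Sample Size and Power) starts from a chart review of 40 patients, in which "the composite primary endpoint rate was 55% in this historical group". It continues "Assuming a 10 percent of composite primary endpoint rate in the treated group and 40 historical controls", and concludes that "14 treated patients are needed to have a 90% power to detect a 45 % difference in the incidence of exacerbation" "at the 5% significance level". Planned enrolment is 20. Neither the sidedness nor the test behind the 14 is given.

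Elsewhere:

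- The Abstract puts the study hypothesis on the composite.
- The Definitions make the composite exacerbation or refractory TTP.
- Section 1.1 gives the primary endpoint as "Incidence of composite primary endpoint, Exacerbation or Refractory TTP".
- Section 1.2.1 opens with "Incidence of Durable Treatment Response" and goes on to days and exchanges to that response, relapse, death and treatment-related adverse events. Exacerbation alone is not listed.
- Section 9.2 says that "Fisher Exact tests will be used to compare the incidence of the composite primary endpoint, Durable Treatment Response, Relapse, treatment-related adverse events" and deaths between treated patients and controls. Exacerbation alone appears in 9.2 only as an outcome in the ADAMTS13 logistic regression.
- Section 2.4, in the background, asks whether the treatment "can shorten the time to treatment response and reduce the risk of exacerbation for patients with TTP".

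**The concern.** The outcome changes name partway through the calculation: the rates going in are composite rates, and the power coming out is for one component. Taken literally, the claim does not follow. If the treated composite rate is 10%, treated exacerbation lies somewhere between 0% and 10%. A 45-point gap then requires a control exacerbation rate of 45% to 55%, meaning 18 to 22 of the 22 historical composite events. The documents do not say how many of the 22 were exacerbations.

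Section 2.4 adds weight, because it also speaks of reducing exacerbation. If exacerbation were the real target, the trial would have a power claim for an outcome with no endpoint listing and no comparison with controls. A reader could then treat a non-significant exacerbation result as a negative finding with 90% power, or read a success on the composite as proof of fewer exacerbations.

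**Working it through.** **Inputs, all from Section 9.1.** Control rate p_c = 0.55 with n_c = 40; treated rate p_t = 0.10; difference 0.55 − 0.10 = 0.45; 5% significance, taken as two-sided because sidedness is not stated; n_t = 14 for 90% power; 20 to be enrolled.

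**Reproducing the plan's figure.** Pooled normal approximation, no continuity correction:

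- p̄ = (n_t·p_t + n_c·p_c)/(n_t + n_c)
- SE₀ = √[p̄(1 − p̄)(1/n_t + 1/n_c)]
- SE₁ = √[p_t(1 − p_t)/n_t + p_c(1 − p_c)/n_c]
- power = Φ[(0.45 − 1.96·SE₀)/SE₁]

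| n_t | p̄ | SE₀ | SE₁ | z | power |
|---|---|---|---|---|---|
| 13 | 23.3/53 = 0.4396 | 0.1585 | 0.1145 | 1.218 | 88.8% |
| 14 | 23.4/54 = 0.4333 | 0.1539 | 0.1123 | 1.321 | 90.7% |
| 20 | 24/60 = 0.4000 | 0.1342 | 0.1034 | 1.809 | 96.5% |

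Fourteen is the smallest number that reaches 90%, so the composite rates return the stated result. The 45 points are the composite difference, and only the noun at the end of the sentence is out of place.

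**With the planned test.** Full enumeration of two-sided Fisher power for 55% vs 10% with 40 controls gives 84.2% at 14 treated, 90.5% at 16 and 94.8% at 20 (one-sided at 20: 96.6%). Planned enrolment therefore covers the composite under the test named in 9.2.

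**What the literal reading would mean.** Suppose c of the 22 historical events (0.55 × 40) were exacerbations. The values of c are assumptions. The table gives two-sided Fisher power for exacerbation alone, 20 vs 40, with the treated rate either scaled by the plan's own ratio, 0.10·c/22, or set at its upper limit of 10%. The last two columns give the chance that the composite is significant and exacerbation alone is not, with a 10% treated composite rate and exacerbations as c/22 of it. Controls are either held at the observed counts or treated as random.

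| c of 22 | power, scaled | power, 10% treated | split result, controls fixed | split result, controls random |
|---|---|---|---|---|
| 22 | 94.8% | 94.8% | 0% | 0% |
| 20 | 91.2% | 89.1% | 2.0% | 4.2% |
| 18 | 85.9% | 79.9% | 6.5% | 9.5% |
| 16 | 78.9% | 67.2% | 16.4% | 16.5% |
| 14 | 70.7% | 52.1% | 35.6% | 24.6% |

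Each row describes a test of exacerbation against controls. Section 9.2 contains no such test.

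**The case for a change.** The strongest case for acting is that the contradiction sits in the sentence that justifies the trial's size, that 2.4 repeats the word, and that in 20 patients the composite and its component can part company. If only 14 of the 22 historical events were exacerbations, power for exacerbation alone would be 52% to 71%, and a split result would occur in roughly a quarter to a third of trials. Changing one phrase would cost almost nothing.

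The mislabel is real, and power for exacerbation alone cannot be derived from the documents; both points stand. The consequences drawn from them do not. A non-significant exacerbation result can arise only if someone runs a comparison that the plan omits. Taking a composite success as evidence on one component is a risk with any composite, and this wording adds little to it. The sums rest on an unreported division of events. At the benign end, 20 to 22 exacerbations, power stays at 89% to 95%. The Definitions also limit the other end: a patient who responds by day 28, stops exchange then and has no recurrence for 30 days reaches a durable response by about day 58, inside the day-60 limit. Leaving aside deaths and departures from the stopping rule, refractory-only events are mainly patients with no response by day 28. The 14-of-22 case needs 8 of 40 controls (20%) in that group, which the documents neither support nor exclude.

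Section 2.4 is a background statement of two aims and makes no power claim. Since exacerbation is part of the composite, it does not compete with the hypothesis in the Abstract.

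**Conclusion.** A clerical slip, with no change to the plan needed. Section 9.1 names the composite for both rates, the 45 points are their difference, and those rates give 14 patients at 90.7% power. The hypothesis, definition, primary endpoint and primary test all point to the same outcome, so an analyst would test the composite without hesitation. Reading the last phrase of the power statement that way leaves the 14, the 20, the Fisher test and any conclusion as they are.

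The 90.7% assumes a two-sided 5% level and the uncorrected pooled formula, which matches the stated 14; the planned two-sided Fisher test has 94.8% at the 20 to be enrolled. The 90% should not be read as applying to exacerbation alone. Showing the two components beside the composite in the report would be ordinary descriptive practice, and the plan does not need amending to allow it.
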